**Design & Procedures** – Adult patients (age > 18 years) who have severe osteoarthritis of the ankle joint significant enough to be treated with a total ankle replacement as determined by Drs. [name], [name], or [name] with the aid of the physical exam and routine radiography, treated at Duke University Medical Center will be asked to participate in this study. After routine surgical counseling by Drs. [name], [name], [name] or [name], those patients meeting the inclusion criteria will be asked to participate in this study by their attending physician. The consent form will be administered in the clinic. No PHI will be collected prior to consent. If a patient chooses to participate, they will be asked to sign the consent form and will be asked to complete the following patient outcome questionnaires (attached): Visual Analog Pain Scale, Short-form 36, AOFAS hind foot score, a Short Musculoskeletal Function Assessment questionnaire and FADI. Also at this time patients will be randomly assigned to receive either the STAR or Salto-Talaris ankle prosthesis at the time of their surgery. There will be 80 individual, sealed, opaque sequentially numbered envelopes containing the randomization of either ankle prosthesis (40 of each implant). The patient will then undergo surgery as scheduled at a later date. Participants will be in the study a total of ten years.

Following surgery, the patient will present for routine follow-up appointments. At the six month, one year, two year, three year visit and every year thereafter, the patients participating in the study will be asked to complete the previously mentioned outcome questionnaires. These are all normal follow-up visit time points; the patients will not be asked to return to clinic for any additional visits that would not be routine. At each visit, the patient will also receive plain x-rays. Plain x-rays are part of routine follow-up and not additional tests for this study.

The study will proceed until a minimum of ten-year follow-up is achieved for all patients. We will leave the ten year window open for all subjects until the last subject has finished their ten year time point. This will ensure that all subjects will have an appropriate time span in order to return for their standard of care visit.

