All patients who receive a total ankle replacement at Duke is asked to complete a set of questionnaires (Visual Analog Scale, Short Musculoskeletal Function Assessment, Short Form-36 Health Survey, Foot and Ankle Outcome Score Questionnaire, AOFAS Ankle-Hindfoot Scale) as part of the Duke Orthopaedics Foot and Ankle physicians' standard of care. We will ask subjects permission to use these questionnaires that have been collected from them since their randomized TAR surgery. We are also asking subjects permission to release their de-identified study information to orthopaedic equipment manufacturers, and to continue their follow-up to their 10-year post-operative time point. A letter will be mailed to all subjects explaining the change. This letter is explained in the Consent Process section. Drs. [name], [name], [name], [name] will only be recruiting their own patients

**Subject identification, recruitment, and compensation**- Inclusion/ Exclusion criteria: Adult patients (age > 18 years) who will benefit from a total ankle replacement, as determined by Drs. [name], [name], [name] or [name], with the aid of the physical exam and routine radiography treated at Duke University Medical Center and who have no medical conditions that would represent contraindications to surgery or anesthesia will be

asked to participate in this study. The only excluded patients will be those who do not choose to participate in this study, have a weight greater than 230lbs, or do not meet the minimum age of 18 years. Drs. [name], [name], or [name] will only be recruiting their own patients. Drs. [name], [name], [name] or [name] will not personally obtain consent due to a conflict of interest related to their consulting relationship with Tornier Inc and SBI Inc. Approximately 100 DUHS patients will be recruited to undergo either a STAR or Salto-Talaris Total Ankle Replacement. Study enrollment will be complete once 50 of each cohort have been treated. There is no compensation associated with participation in this study.

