**Data Analysis & Statistical Considerations** – The data will be summarized using routine descriptive statistics. The following clinical outcome parameters will be analyzed using a series of 2X4 between subject repeated measures ANOVAs, with Tukey post hoc testing to determine statistically significant differences. The 2 X 4 ANOVA will be comparing the 2 groups (Salto Talaris and STAR implants) and the five time points of interest (pre-op, 6 months, 1 year, 2 years, and 3 years following surgery). The clinical outcome variables of interest will be the visual analog pain scale, foot and ankle disability index, the SF-36, the AOFAS hind foot score, and the short form musculoskeletal assessment. In addition, radiographic measurements will be collected on the radiographs that are available in the patients' medical record at each of the pre and post-operative time points. Monitoring of data will not be done until the final analysis after all data is collected. A p-value less than 0.05 will be used as the level of statistical significance for this study.

**Data & Safety Monitoring** - Monitoring data for safety is a function of the PI and study team. The PI will be responsible for review and sign off on all adverse events and/or problems as they occur and report adverse events and/or problems as required by HRPP policies to the IRB.

**Data storage & confidentiality** – The principal investigator and co-investigators will collect data in a computerized database using a commercially available database program. During collection, data will be indexed by the patient's medical record number. After data collection, a case number will be assigned to the data, and the medical record number (the only identifying data collected) will be stripped from the database. The code linking medical record number to case number will be kept in a locked file with access limited to the primary investigator. When the study is complete the code linking medical record numbers to case numbers will be destroyed. During data collection and review protected health information will be available only to the principal investigator and co-investigators and will not be reused or disclosed to any other person or entity, except as required by law, for authorized oversight of the research study.

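### The repeated-measures ANOVA with Tukey tests is planned with no provision for non-sphericity, so the 5% level is not assured for within-patient tests

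*Combined protocol and SAP*

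**What the plan says.** Data Analysis & Statistical Considerations is the whole statistical plan. It specifies "a series of 2X4 between subject repeated measures ANOVAs, with Tukey post hoc testing to determine statistically significant differences", with two implant groups and five visits: pre-op, 6 months, 1, 2 and 3 years. The same analysis is applied separately to "the visual analog pain scale, foot and ankle disability index, the SF-36, the AOFAS hind foot score, and the short form musculoskeletal assessment". The threshold is set in one sentence: "A p-value less than 0.05 will be used as the level of statistical significance for this study".

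The section does not mention sphericity, an epsilon correction, a multivariate test or a covariance structure. It does not say which means the Tukey tests compare or which error term they use. No SD or within-patient correlation is given anywhere.

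The design label has four time levels but five visits are listed. The calculations below use the five listed visits.

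**The concern.** In a classical univariate repeated-measures ANOVA, the F tests for visit and for group-by-visit have their nominal level only under sphericity, that is, when the difference between any two visits has the same variance. Tukey tests of visit means that use the single pooled within-patient error term need the same condition.

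There is reason to doubt it here. Surgery falls between the first and second visits, and the gaps between visits run from 6 months to a year. Pre-op scores may well correlate less with post-op scores than post-op scores do with each other, and correlation may fall as visits move apart.

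The group-by-visit test is at stake. Both arms receive a replacement, so this is the test that shows whether the implants follow different courses after surgery. If it runs above 5% it will too often declare a difference that is not there, and the same gap affects all five scales. With a pooled error term, some visit contrasts would also look more precise than they are and others less.

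**Working it through.** **Is there a figure to reproduce?** No. The 0.05 is a declared threshold. The level attained depends on a covariance that the documents do not give, so it can only be examined over assumed structures.

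**Inputs from the documents.** Two groups; visits at 0, 0.5, 1, 2 and 3 years; threshold 0.05. Design & Procedures provides 80 envelopes, 40 per implant, while the recruitment section says "Study enrollment will be complete once 50 of each cohort have been treated". Both 40 and 50 per arm were therefore run. Degrees of freedom for group-by-visit are 4 and 4 × (N − 2), which is 312 at N = 80 and 392 at N = 100.

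**Assumptions.** Complete, normally distributed data with no implant or visit effect; 8,000 simulated trials per case, with simulation error of about ±0.5 percentage points. Tukey tests are taken to compare visit means with one pooled error term. The covariances are those in the table below.

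**Departure from sphericity.** Box's epsilon is (sum of eigenvalues)² / [4 × sum of squared eigenvalues] of the covariance of the four orthonormal visit contrasts; 1 means sphericity. Take SDs of 1, a pre-op to post-op correlation of 0.3 and a correlation of 0.7 among post-op visits:
- Three eigenvalues equal 1 − 0.7 = 0.3.
- The fourth, pre-op against the post-op mean, is 0.8 × [1 + (1 + 3 × 0.7)/4 − 2 × 0.3] = 0.94.
- Epsilon = (0.9 + 0.94)² / [4 × (0.27 + 0.8836)] = 3.3856/4.6144 = 0.73.

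**Simulated type I error.**

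| Assumed structure | Epsilon | Group-by-visit, uncorrected | Any Tukey visit contrast |
|---|---|---|---|
| Equal correlation 0.5, equal SDs | 1.00 | 5.0–5.2% | 4.6–5.2% |
| Correlation decaying with time (0.8, 0.6 or 0.4 per year), equal SDs | 0.57–0.77 | 6.4–8.3% | 5.8–7.0% |
| Pre-op less correlated (0.3 v 0.6, 0.3 v 0.7, 0.2 v 0.8), equal SDs | 0.53–0.86 | 5.6–8.9% | 6.1–8.8% |
| Pre-op less correlated (0.3 v 0.6, 0.4 v 0.6), pre-op SD 0.7 or 0.6 of post-op | 0.96–1.00 | 4.7–5.3% | 4.8–5.6% |
| Equal correlation 0.5, pre-op SD 0.6 of post-op | 0.97 | 5.0–5.7% | 4.8–5.4% |

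Across all these cases the Greenhouse-Geisser corrected group-by-visit test stayed at 4.4–5.3%, and the implant main-effect test at 4.4–5.6%.

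**Standard errors under pooling.** With equal SDs, the ratio of true to pooled SE for visits i and j is √[(1 − ρij)/(1 − mean ρ)]. Above 1, the pooled SE is too small.
- *Pre-op 0.3, post-op 0.7.* Mean ρ = (4 × 0.3 + 6 × 0.7)/10 = 0.54. Pre-op contrasts: √(0.70/0.46) = 1.23, too small. Post-op contrasts: √(0.30/0.46) = 0.81, too large.
- *Decay of 0.7 per year.* Mean ρ = 0.609. Pre-op v 6 months: √[(1 − 0.837)/0.391] = 0.65. Pre-op v 1 year: √(0.30/0.391) = 0.88. Pre-op v 2 years: √(0.51/0.391) = 1.14. Pre-op v 3 years: √(0.657/0.391) = 1.30. The pooled SE is too large for the first two and too small for the last two.
- *Equal correlation 0.5, pre-op SD 0.6.* The variance of a pre-op difference is 0.36 + 1 − 0.6 = 0.76, and of a post-op difference 1.0. The average is (4 × 0.76 + 6 × 1.0)/10 = 0.904. Pre-op contrasts: √(0.76/0.904) = 0.92, too large.

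**The case against.** The strongest reply is that this is under-specification, not a demonstrated error. The text does not exclude a corrected or multivariate test, which software may supply by default, and it does not say that Tukey uses a pooled error term. That stands. It leaves the gap open, however: if the choice is left to the software or the analyst, the test can be picked after the data are seen.

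A reader might draw four stronger conclusions that the documents do not support.

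- *That the 5% level fails.* This depends on a covariance the documents do not give. Unequal spacing alone does not break sphericity: with equal correlations the level was 5.0–5.2% at these same visits. A smaller pre-op SD can bring it back to about 5%.
- *That standard errors for pre-op contrasts are always too small.* The direction depends on the correlations and SDs, as the last two examples in the working show.
- *That a single contrast rejects at well above 5%.* That follows only if the inflated SE is set against 1.96. The plan names Tukey, whose critical value for five means is about 2.74 (nominal 0.6% per contrast). With SE factors of 1.26 to 1.32 the per-contrast error is about 3.0–3.8%: well above 0.6%, but below 5%. Family-wise error is the relevant measure.
- *That the implant comparison as a whole is invalid.* The main-effect test does not depend on sphericity. It is still a poor substitute for the interaction, because it averages in the pre-op visit. A constant post-op difference δ would appear as 4δ/5 = 0.8δ.

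It is also fair to say that Greenhouse-Geisser alone repairs the group-by-visit test, so the full model is the better option rather than the only acceptable one. An epsilon correction does not, however, repair contrasts that share a pooled error term.

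**Conclusion.** The point holds as a gap in the plan. The 5% level is not assured for the visit and group-by-visit tests. Uncorrected, group-by-visit runs at about 6% to 9% under the assumed non-spherical structures with equal SDs, and at about 5% when sphericity holds or nearly holds. If Tukey visit contrasts use one pooled error term, their family-wise error is also about 6% to 9% in those non-spherical cases, and individual standard errors are wrong in a direction that cannot be known in advance. The implant main-effect test is unaffected.

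The sizes rest on assumed correlations and SDs, complete normal data, five visits and 40 or 50 per arm. The inflation is moderate and conditional, but it can be prevented with a few sentences before the analysis, so the change should be made.

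**What to change.** Replace the ANOVA sentence with a likelihood-based repeated-measures model for each outcome: implant, visit and implant-by-visit as fixed effects, unstructured within-patient covariance, and Kenward-Roger degrees of freedom. Report the implant difference at each visit from that model with its 95% CI. This needs no sphericity assumption and gives each contrast its own standard error.

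If ANOVA is kept, require the Greenhouse-Geisser correction for the visit and group-by-visit tests. Replace pooled Tukey tests with contrasts that use their own error terms and a stated multiplicity adjustment.

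The cost is SAP wording; standard software does both. The unstructured model estimates 5 × 6/2 = 15 covariance parameters, which 80 to 100 patients support, and it gives up a little power if sphericity does hold. The plan defers analysis until all data are collected, so the text can be settled before any results are seen.

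### The ANOVA is labelled 2X4 but lists five time points with pre-op as an outcome level, names no deciding instrument or contrast, and does not use the pre-op score as a covariate

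*Combined protocol and SAP*

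**What the plan says.** Data Analysis & Statistical Considerations specifies a "series of 2X4 between subject repeated measures ANOVAs, with Tukey post hoc testing to determine statistically significant differences". It repeats the 2 X 4 label, then describes the design as two implant groups by "the five time points of interest (pre-op, 6 months, 1 year, 2 years, and 3 years following surgery". Pre-op is therefore listed as a level of the time factor.

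Five instruments are to be analysed: "The clinical outcome variables of interest will be the visual analog pain scale, foot and ankle disability index, the SF-36", plus the AOFAS hindfoot score and the short musculoskeletal assessment. None is called primary. The only decision rule is "A p-value less than 0.05 will be used as the level of statistical significance for this study".

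No covariate is mentioned anywhere. Yet Design & Procedures has patients complete all five questionnaires at consent, when they are also randomised, and again at every study follow-up visit.

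The sample size appears twice: 40 per implant in the envelope description (Design & Procedures), and "Study enrollment will be complete once 50 of each cohort have been treated" (Subject identification, recruitment, and compensation).

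**The concern.** Two analysts could build different models from this paragraph: one with five outcome levels including pre-op, one with the four post-op visits only. Either could then rest the implant conclusion on the group main effect, the group-by-time interaction or a Tukey contrast, on any of five instruments.

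Two things are at stake. The first is precision. An implant cannot affect a score taken before surgery, so averaging that score into the group effect dilutes the difference, and its correlation with later scores goes unused. The second is error control. If several results are equally entitled to decide, the chance that at least one crosses 0.05 with no true difference exceeds 5%.

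**Working it through.** **Layout.** Two groups by five listed times (pre-op, 6 months, 1, 2 and 3 years) is 2x5. The 2X4 label fits only if pre-op is dropped, which contradicts the list. The plan gives no power, SD, correlation or effect size, so there is no power figure to reproduce.

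**Assumptions (not in the documents).** SD 1 at every visit; pre/post correlation c = 0.3-0.5, with 0.1 as a low case; post/post correlation r = 0.5-0.7; complete data; two-sided 0.05. From the documents: n = 50 or 40 per arm.

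**If the five-level main effect decides.** A constant post-op difference d is estimated as (0 + 4d)/5 = 0.8d. Let vp = (1+3r)/4, the variance of a patient's four-visit post-op mean.
- Main effect, rescaled to the post-op mean difference: variance (2/n)(vp + c/2 + 1/16).
- Baseline-adjusted post-op mean: variance (2/n)(vp - c²).
- Gap: (2/n)(c + 1/4)², never negative, whatever the size or shape of the difference.

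| c, r | main effect | adjusted | ratio |
|---|---|---|---|
| 0.1, 0.5 | 0.7375 | 0.615 | 1.20 |
| 0.1, 0.7 | 0.8875 | 0.765 | 1.16 |
| 0.3, 0.5 | 0.8375 | 0.535 | 1.57 |
| 0.3, 0.7 | 0.9875 | 0.685 | 1.44 |
| 0.5, 0.5 | 0.9375 | 0.375 | 2.50 |
| 0.5, 0.7 | 1.0875 | 0.525 | 2.07 |

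For a sustained 0.5 SD difference (noncentral t, c = 0.3-0.5), main effect against adjusted mean: 66-77% v 85-98% at 50 per arm; 56-68% v 76-95% at 40 per arm.

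**If one visit's unadjusted between-implant contrast decides.** Adjustment multiplies its variance by 1 - c²: a cut of 1% at c = 0.1, 9% at 0.3 and 25% at 0.5.

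**If only the four post-op visits were meant.** Sustained 0.5 SD, 50 per arm: the unadjusted mean has 80-88% power. Adjustment raises this by under 1 point at c = 0.1 (80.3 to 80.8%; 87.9 to 88.4%) and by up to about 12 points at c = 0.5 (80.3 to 92.7%).

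**If group-by-time decides.** The like-for-like replacement is a baseline-adjusted joint 4-df test of the implant differences at the four post-op visits. Its noncentrality is (n/2)·δ'S⁻¹δ, where δ holds the four visit differences and S = (1-r)I + (r-c²)J (I the identity, J all ones). For a sustained 0.5 SD at n = 50 this is 25/(1+3r-4c²): 11.68, 9.12, 16.67 and 11.90 for the last four rows above. The planned interaction was simulated.

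Power, 50 per arm, 0.5 SD at its largest, c = 0.3-0.5:

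| Shape | main effect | planned group-by-time | adjusted mean | adjusted 3-year | adjusted joint test |
|---|---|---|---|---|---|
| sustained | 66-77% | about 60-77% | 85-98% | 74-82% | 64-91% |
| 2 and 3 years only | 22-27% | about 83-97% | 32-52% | 74-82% | 88-98% |
| growing to 3 years | 25-31% | about 52-73% | 37-59% | 74-82% | 61-78% |

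For a difference at 6 months and 1 year only, the figures match the second row, except that the 3-year contrast has 5%.

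**Error control, no true difference.** Main effect or interaction below 0.05 on one instrument: 9.7-10.9% by simulation (9.3-9.7% with Greenhouse-Geisser correction). One test on each of five instruments: 1 - 0.95⁵ = 22.6% if independent, falling to 12.8% at an assumed between-instrument correlation of 0.8.

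**The case against.** The plan is not silent on testing: Tukey is a named procedure that points to pairwise contrasts, and the five visits are spelled out, so the label alone is a small slip. The patient multiplier applies only if the main effect decides, which the plan does not say. It also depends on unknown correlations: about 1.2 at a pre/post correlation of 0.1, but 1.1875/0.285 = 4.2 when c = r = 0.7. Equal variance before and after surgery is a further assumption. And where the difference is late, growing or early, the planned group-by-time test beats the adjusted average.

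Most of this stands, and it limits the point. What is missing is the contrast and the instrument, not a procedure. The power objection compares tests of different type, though. Like for like, adjustment does not lose: the variance gap is never negative, a single-visit variance falls by c², and the adjusted joint test has about the same or higher power than the interaction.

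A reader might infer more than the documents support:
- That the planned ANOVA is biased or invalid. It is not: randomisation makes pre-op scores equal in expectation, so each test stands on its own, given the usual sphericity correction for the interaction.
- That the trial needs up to 2.5 times as many patients. That holds only for the main-effect reading at the correlations shown.
- That an averaged adjusted contrast is always best. Against group-by-time it is better only for a sustained difference.
- That no comparison by arm can have been made. The plan says "Monitoring of data will not be done until the final analysis after all data is collected", which concerns monitoring; the documents do not show whether arms have been compared.

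**Conclusion.** The point holds in this limited form. The mismatch between 2X4 and five time points, the undefined deciding result and the absence of baseline adjustment follow from the text without any assumption. The size of the precision loss depends on which test decides and on assumed correlations: it runs from negligible (a single-visit contrast, or the four post-op visits alone, at correlation 0.1) to substantial (the five-level main effect at 0.3-0.5). The direction is the same under both sample sizes. The error-control problem does not depend on the baseline argument: about 10% on one instrument if either ANOVA effect may decide, and 13-23% across five instruments with one test each. This should be fixed, but it does not invalidate the trial.

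**What to change.** Make a dated amendment before any comparison by arm. Scores already exist ("We will ask subjects permission to use these questionnaires that have been collected from them since their randomized TAR surgery"), so the sponsor must confirm that no such comparison has been made; otherwise the analysis should be labelled post hoc.

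1. Correct the layout: four post-op visits as outcomes, pre-op score as covariate.
2. For each outcome, fit a linear mixed model with implant, visit, implant-by-visit, pre-op score and pre-op-by-visit, and unstructured covariance. Include every randomised patient with at least one post-op score, in the arm assigned. Keep those with no pre-op score (overall pre-op mean plus a missing indicator, or a constrained longitudinal model with a common pre-op mean).
3. Name one primary instrument, one score from it, and one deciding test at 0.05: the adjusted average over four visits, the adjusted 3-year difference, or the adjusted joint test, according to the question. The other instruments are supportive.
4. Report adjusted per-visit differences with 95% CIs in place of Tukey tests, and state the missing-at-random assumption.

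The cost is amendment wording and the choice of instrument and test. No new visits or forms are needed, since Design & Procedures requires all five instruments at each study visit. The standard-of-care set described there ("Visual Analog Scale, Short Musculoskeletal Function Assessment, Short Form-36 Health Survey, Foot and Ankle Outcome Score Questionnaire, AOFAS Ankle-Hindfoot Scale") omits the FADI, so check its completeness before making it primary. The downsides are slightly more modelling, reliance on missing at random, and lower power for effect shapes the chosen test does not target: 32-52% for a late difference if the average is chosen, and no real power for an early difference that fades if the 3-year contrast is chosen.

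### Tukey family undefined: if it spans all implant-by-visit cells, it corrects for 45 pairs to test 4 useful implant contrasts and lowers power at each visit

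*Combined protocol and SAP*

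**What the plan says.** All of the relevant text is in Data Analysis & Statistical Considerations, apart from the sample size.

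- **Model:** "a series of 2X4 between subject repeated measures ANOVAs", one per instrument.
- **How significance is reached:** "with Tukey post hoc testing to determine statistically significant differences".
- **Factors:** two implants, and "the five time points of interest (pre-op, 6 months, 1 year, 2 years, and 3 years following surgery". Five visits do not match the 2X4 label.
- **Level:** "A p-value less than 0.05 will be used as the level of statistical significance for this study". Sidedness is not given.
- **Outcomes:** five instruments ("The clinical outcome variables of interest will be the visual analog pain scale, foot and ankle disability index, the SF-36, the AOFAS hind foot score"; a musculoskeletal function questionnaire is the fifth). None is named primary, and no visit is named primary.
- **Sample size:** Design & Procedures has envelopes for "40 of each implant". The recruitment section says "Study enrollment will be complete once 50 of each cohort have been treated".

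The plan does not say whether Tukey compares the implant-by-visit cells, the two implant means or the visit means. Nor does it say whether the implant question is settled by an ANOVA F test or by the post hoc contrasts. It gives no power, effect size or standard deviation.

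**The concern.** The trial is randomised to compare two implants. In a two-by-five layout, the pairs that show where the implants differ are those taken at the same post-operative visit. Tukey over all cells also protects visit-to-visit pairs within one implant, and pairs that set one implant at one visit against the other implant at a different visit. Neither kind says which implant does better, but both raise the threshold that every same-visit implant contrast must pass.

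The other readings of the sentence do not help. With two implant means, Tukey is a single comparison and repeats the ordinary test. With visit means pooled over implants, it says nothing about the implants. The cell-level reading is therefore the one on which Tukey can locate an implant difference by visit, and it is also the one that carries the penalty. At stake is a real difference at a visit being reported as non-significant in a trial of 80 to 100 patients.

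**Working it through.** The plan states no power figure, so there is nothing to reproduce.

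**Inputs from the plan:** 2 implants; 5 listed visits, 4 of them post-operative; alpha 0.05; n = 50 or 40 per implant.

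**Assumed:** two-sided tests; complete data; the ordinary two-group standard error at one visit; a true difference d of 0.6 SD, with other values shown below.

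**1. Count of pairs.** Five visits: 2 × 5 = 10 cells, and 10 × 9 / 2 = 45 pairs. Five of these compare the implants at the same visit, 4 of them after surgery. Under the 2X4 label: 8 cells, 8 × 7 / 2 = 28 pairs, of which at most 4 are post-operative implant contrasts.

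**2. Critical t.**
- Tukey: the 95% point of the studentised range divided by √2. Error df = (2n − 2) × (visits − 1), which at n = 50 is 98 × 4 = 392 for 10 cells and 98 × 3 = 294 for 8 cells. At n = 40 it is 312 and 234.
- Bonferroni over four contrasts: two-sided t at 0.05/4 = 0.0125, df 2n − 2 (98 or 78).
- Single contrast: two-sided t at 0.05, same df.

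**3. Smallest difference that can be declared.** Critical t × √(2/n), where √(2/50) = 0.200 SD and √(2/40) = 0.224 SD.

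**4. Power.** Noncentral t with noncentrality d / √(2/n). At d = 0.6 this is 0.6/0.200 = 3.00 for n = 50 and 0.6/0.224 = 2.68 for n = 40.

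| | Tukey, 10 cells | Tukey, 8 cells | Bonferroni, 4 contrasts | Single contrast |
|---|---|---|---|---|
| Critical t, n = 50 | 3.18 | 3.05 | 2.55 | 1.98 |
| Smallest declarable difference, n = 50 | 0.64 SD | 0.61 SD | 0.51 SD | 0.40 SD |
| Power at d = 0.6, n = 50 | 43% | 48% | 68% | 84% |
| Power at d = 0.6, n = 40 | 32% | 36% | 55% | 76% |

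**5. Sensitivity to the effect size** (n = 50, Tukey over 10 cells against Bonferroni over 4): 26% against 49% at d = 0.5; 63% against 83% at d = 0.7; 79% against 93% at d = 0.8.

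**6. Error actually spent on the implant contrasts.** Tukey over 10 cells tests each pair at about 0.0016. Over the four post-operative implant contrasts that is at most 4 × 0.0016 ≈ 0.006, against the 0.05 that the plan allows.

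**The case against.** **The family is not stated.** A reader might infer that the plan commits to 45 comparisons. It does not. The cell-level reading is natural, because Tukey is attached to the crossed ANOVA, but it remains an inference. This stands, and the conclusion is conditional on it.

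**Power for the implant question as a whole is not halved.** A reader might infer that it is, because 84% falls to 43% at d = 0.6 and n = 50. That compares Tukey with an unadjusted contrast, which nobody proposes here. Against the four-contrast correction the fall is from 68% to 43%. The ANOVA F tests also carry no Tukey penalty. With d = 0.56, n = 50, a constant post-operative effect and within-patient correlation of 0.3 to 0.7 (all assumed), the group main effect has about 92% to 73% power even with the pre-operative visit averaged in. In the same setting, power to find a difference at any of the four visits is 93% to 83% with Bonferroni and 73% to 58% with Tukey, a loss of 20 to 24 points. This stands. However, the main effect includes a visit at which no implant is in place, and neither F test says at which visit the implants differ.

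**Five instruments need more correction than four contrasts.** Five instruments × 4 visits = 20 implant contrasts. Bonferroni over 20 gives a critical t of 3.10 and 46% power at d = 0.6 and n = 50, close to Tukey's 3.18 and 43%. It is therefore wrong to say that narrowing the family costs only visit-to-visit protection. But Tukey is applied within each instrument and does not target that multiplicity. The similar threshold is a coincidence.

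**The error term matters.** If software applied Tukey with the within-patient error, the standard error would shrink by √(1 − ρ), where ρ is the within-patient correlation. At ρ = 0.5 the declarable difference is 3.18 × 0.200 × √0.5 = 0.45 SD, and power would appear higher. That standard error is wrong for comparing different patients, so it does not defend the plan. It does mean that the fix must name the error term.

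**Change over time may be of interest.** The background section describes evaluating ankle replacement as such. This is a reason to report change over time, which the fix does.

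**Conclusion.** The concern holds as a conditional one. The plan makes Tukey testing the route to significance and leaves its family undefined. If the family is all implant-by-visit cells, power for one same-visit implant contrast at 0.6 SD is about 43% (n = 50) or 32% (n = 40), against 68% or 55% with a correction confined to the four post-operative implant contrasts. Under the 28-pair reading the Tukey figures are 48% and 36%, so the loss does not depend on how the 2X4 label is resolved.

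These figures rest on an assumed effect size, complete data and the correct two-group standard error. The gap narrows as the effect grows. They describe a contrast at a single visit and do not support a claim about every test of the implant effect. This is a cheap and worthwhile improvement to the analysis; it does not invalidate the plan.

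**What to change.** In Data Analysis & Statistical Considerations, replace the clause "with Tukey post hoc testing to determine statistically significant differences" with wording such as: *the implants will be compared by planned contrasts at each of the four post-operative visits, from the same model, with standard errors appropriate to between-patient comparisons and Holm adjustment over those four contrasts within each instrument; change over time within each implant will be given as estimates with confidence intervals.* Holm never rejects less than Bonferroni, so the Bonferroni figures above are a floor for this approach.

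Correct the 2X4 label to match the visits listed, and reconcile 40 with 50 per implant. The fix does not depend on either.

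**Cost:** one sentence and no extra data. Formal multiplicity protection for visit-to-visit comparisons is given up, and each implant contrast faces a looser threshold than under all-cells Tukey. Multiplicity across the five instruments stays uncontrolled, as it is now: with 0.05 spent per instrument, the bound over all five is 5 × 0.05 = 0.25.
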